9.2.1.2 Tumor Imaging During the Study

Note: As of Amendment 03, central review of images and iRECIST are no longer applicable. After the first on-study imaging assessment at Week 9, further imaging will be performed as per local SoC guidelines however the data will not be collected. This section has been updated accordingly.

The first on-study imaging assessment should be performed at 9 weeks (63 days \pm 7 days) from the date of randomization. No further imaging is mandated; any further imaging for disease assessments will be performed by site investigator/radiology assessment as per local SoC guidelines; only the date of scans performed as per SoC needs to be documented in the eCRF. Imaging timing should follow calendar days and should not be adjusted for delays in cycle starts. If the bone scan is positive at baseline, bone scans should be performed as per local SoC guidelines; the results will not be monitored, only the date of scans performed as per SoC needs to be documented in the eCRF.

9.2.1.3 End of Treatment and Follow-up Tumor Imaging

Note: As of Amendment 03, there is no protocol specified imaging after the Week 9 assessment for efficacy analysis. This section has been updated accordingly.

For participants who discontinue study treatment before the Week 9 imaging assessment for efficacy analysis, tumor imaging should be performed at the time of treatment discontinuation (\pm 4 week window). If previous imaging was obtained within 4 weeks prior to the date of discontinuation, then imaging at treatment discontinuation is not mandatory. For participants who discontinue study treatment due to documented disease progression, this is the final required tumor imaging.

9.2.1.4 Second Course Phase Tumor Imaging

Note: As of Amendment 03, the text in this section is no longer applicable; disease assessment will be performed by the investigator per local SoC guidelines; results will not be collected, only the date of scans performed as per SoC needs to be documented in the eCRF.

Tumor imaging (including bone scan) must be performed within 28 days prior to restarting treatment with pembrolizumab + epacadostat/matching placebo. Local reading (Investigator assessment with site radiology reading) will be used to determine eligibility. Second Course imaging can be submitted to the central imaging vendor for quality control, storage, and possible retrospective review.

The first on-study imaging assessment should be performed at 12 weeks (84 days \pm 7 days) after randomization. Subsequent tumor imaging should be performed every 12 weeks (84 days \pm 7 days) or more frequently if clinically indicated.

Per RECIST 1.1 (Section 9.2.1.5) if tumor imaging shows initial PD, tumor assessment should be repeated 4 to 8 weeks later in order to confirm PD with the option of continuing treatment

while awaiting radiologic confirmation of progression. Participants who obtain confirmatory imaging do not need to undergo scheduled tumor imaging if it is less than 4 weeks later and may wait until the next scheduled imaging time point if clinically stable.

Imaging should continue to be performed until disease progression, the start of a new anticancer treatment, withdrawal of consent, death, or notification by the MSD, whichever occurs first. In clinically stable participants, disease progression may be confirmed by the Investigator using iRECIST 4 to 8 weeks after the first tumor imaging indicating PD.

For participants who discontinue Second Course study treatment, tumor imaging should be performed at the time of treatment discontinuation (± 4 week window). If previous imaging was obtained within 4 weeks prior to the date of discontinuation, then imaging at treatment discontinuation is not mandatory. For participants who discontinue study treatment due to documented disease progression, this is the final required tumor imaging.

For participants who discontinue Second Course study treatment without documented disease progression, every effort should be made to continue monitoring disease status by radiologic imaging every 12 weeks (84 days \pm 7 days) until either the start of a new anticancer treatment, disease progression, death, or the end of the study, whichever occurs first.

9.2.1.5 RECIST 1.1 Assessment of Disease

RECIST 1.1 will be used by the Investigator as the primary measure for assessment of tumor response, date of disease progression, and as a basis for all protocol guidelines related to disease status (eg, discontinuation of study treatment). Although RECIST 1.1 references a maximum of 5 target lesions in total and 2 per organ, this protocol allows a maximum of 10 target lesions in total and 5 per organ, if clinically relevant to enable a broader sampling of tumor burden.

9.2.1.6 iRECIST Assessment of Disease

Note: As of Amendment 03, this section is no longer applicable; iRECIST data will no longer be collected. Participants with radiographic disease progression as determined by RECIST 1.1 will discontinue from the study and be followed for safety monitoring, as detailed in Section 9.3; no confirmatory scans are required.

iRECIST is based on RECIST 1.1, but adapted to account for the unique tumor response seen with immunotherapeutic drugs. iRECIST will be used by the Investigator to assess tumor response and progression and make treatment decisions. When clinically stable, participants should not be discontinued until progression is confirmed by the Investigator, working with local radiology, according to the rules outlined in Appendix 7. This allowance to continue treatment despite initial radiologic PD takes into account the observation that some participants can have a transient tumor flare in the first few months after the start of immunotherapy, and then experience subsequent disease response. This data will be captured in the clinical database.

Clinical stability is defined as the following:

- Absence of symptoms and signs indicating clinically significant progression of disease
- No decline in ECOG performance status

- No requirements for intensified management, including increased analgesia, radiation, or other palliative care

Any participant deemed clinically unstable should be discontinued from study treatment at site-assessed first radiologic evidence of PD, and is not required to have repeat tumor imaging for confirmation of PD by iRECIST.

If the Investigator decides to continue treatment, the participant may continue to receive study treatment and the tumor assessment should be repeated 4 to 8 weeks later to confirm PD by iRECIST, per Investigator assessment. Images should continue to be sent in to the central imaging vendor for potential retrospective BICR.

If repeat imaging does not confirm PD per iRECIST, as assessed by the Investigator, and the participant continues to be clinically stable, study treatment may continue and follow the regular imaging schedule. If PD is confirmed, participants will be discontinued from study treatment.

If a participant has confirmed radiographic progression (iCPD) as defined in Appendix 7, study treatment should be discontinued; however, if the participant is achieving a clinically meaningful benefit, an exception to continue study treatment may be considered following consultation with the Sponsor. In this case, if study treatment is continued, tumor imaging should continue to be performed following the intervals as outlined in Section 2 and submitted to the central imaging vendor.

A description of the iRECIST process is provided in Appendix 7, with additional details in the iRECIST publication [Seymour, L., et al 2017]. A summary of imaging and treatment requirements after first radiologic evidence of progression is provided in [Table 7](#).

Table 7 Imaging and Treatment after First Radiologic Evidence of Progressive Disease

	Clinically Stable		Clinically Unstable	
	Imaging	Treatment	Imaging	Treatment
First radiologic evidence of PD by RECIST 1.1 which has been verified by Investigator	Repeat imaging at 4 to 8 weeks to confirm PD	May continue study treatment at the Investigator's discretion while awaiting confirmatory tumor imaging by site by iRECIST.	Repeat imaging at 4 to 8 weeks to confirm PD per Investigator's discretion only	Discontinue treatment
Repeat tumor imaging confirms PD (iCPD) by iRECIST per Investigator assessment	No additional imaging required	Discontinue treatment (exception is possible upon consultation with MSD)	No additional imaging required	Not applicable
Repeat tumor imaging shows iUPD by iRECIST per Investigator assessment	Repeat imaging at 4 to 8 weeks to confirm PD. May occur at next regularly scheduled imaging visit.	Continue study treatment at the Investigator's discretion.	Repeat imaging at 4 to 8 weeks to confirm PD per Investigator's discretion only.	Discontinue treatment
Repeat tumor imaging shows iSD, iPR or iCR by iRECIST per investigator assessment	Continue regularly scheduled imaging assessments	Continue study treatment at the investigator's discretion	Continue regularly scheduled imaging assessments	May restart study treatment if condition has improved and/or clinically stable per investigator's discretion. Next tumor imaging should occur according to the regular imaging schedule

iCPD = iRECIST confirmed progressive disease; iCR = iRECIST complete response; iRECIST = Modified Response Evaluation Criteria in Solid Tumors 1.1 for Immune-based Therapeutics; iSD = iRECIST stable disease; iUPD = iRECIST unconfirmed progressive disease; PD = progressive disease; RECIST 1.1 = Response Evaluation Criteria in Solid Tumors 1.1.

Note: If progression has been verified by the Investigator, further management by the site should be based on iRECIST. Any further imaging should still be submitted to the central imaging vendor, for possible retrospective review.

9.2.2 Patient Reported Outcomes

Note: As of Amendment 03, PROs will no longer be collected after the first on-study imaging assessment at Week 9.

The EuroQoL EQ-5D and EORTC QLQ-C30 questionnaires will be administered by trained site personnel and completed electronically by participants in the following order: EuroQoL EQ-5D first, then EORTC QLQ-C30. The questionnaires should be administered prior to dosing at Cycle 1-4, then every 3rd cycle through 12 months (ie, Cycles 7, 10, 13, 16), then every 4th cycle after 12 months until EOT (ie, Cycles 20, 24, 28, 32), at Discontinuation, and at the 30-day Safety Follow-up Visit.

It is best practice and strongly recommended that electronic PRO (ePROs) are administered to randomized participants prior to drug administration, AE evaluation, and disease status notification. If the subject does not complete the ePROs at a scheduled time point, the MISS_MODE form must be completed to capture the reason the assessment was not performed.

9.2.3 Survival Follow-up

NOTE: As of Amendment 03, this section is no longer applicable. Participants currently in survival follow-up are considered to have completed the study; these participants will no longer be contacted for survival information. Assessment and recording of AEs will continue as per Section 9.3.

Once a participant experiences Investigator-confirmed PD or starts a new anti-cancer therapy, the participant moves into the Survival Follow-Up Phase and should be contacted by telephone approximately every 12 weeks \pm 7 days to assess survival status until death, withdrawal of consent, or the end of the study, whichever occurs first. Post-study treatments and the participant's response to them will also be collected.

If a participant withdraws consent for treatment and/or imaging, the participant should still be followed for survival unless they specifically withdraw their consent for survival follow-up. Participants should be encouraged to remain in the Survival Follow-Up Phase and sites should ensure the participant understands the non-invasive nature of this phase.

MSD will request survival status to be assessed at additional time points during the course of the study. For example, survival status may be requested prior to an external DMC safety review, efficacy interim analyses, and final analysis. All participants who are in the Follow-Up and Survival Follow-Up Phases and not known to have died prior to the request for these additional survival status time points will be contacted at that time.

9.3 Adverse Events (AE), Serious Adverse Events (SAE) and Other Reportable Safety Events

The definitions of an adverse event (AE) or serious adverse event (SAE), as well as the method of recording, evaluating, and assessing causality of AE and SAE and the procedures for completing and transmitting AE, SAE and other reportable safety event reports can be found in Appendix 3. Progression of cancer under study is not considered an adverse event as described in Appendix 3.

AE, SAEs, and other reportable safety events will be reported by the participant (or, when appropriate, by a caregiver, surrogate, or the participant's legally authorized representative).

The investigator, who is a qualified physician, and any designees are responsible for detecting, assessing, documenting, and reporting events that meet the definition of an AE or SAE as well as other reportable safety events. Investigators remain responsible for following up AE, SAEs and other reportable safety events for outcome according to Section 9.3.3.

Adverse events will not be collected for participants during the pre-screening period (for determination of archival tissue status) as long as that participant has not undergone any protocol-specified procedure or intervention. If the participant requires a blood draw, fresh tumor biopsy etc., the participant is first required to provide consent to the main study and AEs will be captured according to guidelines for standard AE reporting.

9.3.1 Time Period and Frequency for Collecting AE, SAE and Other Reportable Safety Event Information

All AEs, SAEs and other reportable safety events that occur after the consent form is signed but before treatment allocation/randomization must be reported by the investigator if the participant is receiving placebo run-in or other run-in treatment, if the event causes the participant to be excluded from the trial, or is the result of a protocol-specified intervention, including but not limited to washout or discontinuation of usual therapy, diet, or a procedure.

- All AEs from the time of treatment allocation/randomization through 90 days following cessation of study treatment, or 30 days following cessation of study treatment if the participant initiates new anticancer therapy, whichever is earlier, must be reported by the investigator.
- All AEs meeting serious criteria, from the time of treatment allocation/randomization through 90 days following cessation of study treatment, or 30 days following cessation of study treatment if the participant initiates new anticancer therapy, whichever is earlier must be reported by the investigator.
- All pregnancies and exposure during breastfeeding, from the time of treatment allocation/randomization through 120 days following cessation of study treatment, or 30 days following cessation of study treatment if the participant initiates new anticancer therapy must be reported by the investigator.
- Additionally, any SAE brought to the attention of an investigator at any time outside of the time period specified above must be reported immediately to MSD if the event is considered to be drug-related.

Investigators are not obligated to actively seek AE or SAE or other reportable safety events in former study participants. However, if the investigator learns of any SAE, including a death, at any time after a participant has been discharged from the study, and he/she considers the event to be reasonably related to the study treatment or study participation, the investigator must promptly notify MSD.

All initial and follow-up AEs, SAEs and other reportable safety events will be recorded and reported to MSD or designee within the timeframes as indicated in [Table 8](#).

Table 8 Reporting Time Periods and Timeframes for Adverse Events and Other Reportable Safety Events

Type of Event	Reporting Time Period: Consent to Randomization/ Allocation	Reporting Time Period: Randomization/ Allocation through Protocol-Specified Follow- up Period	Reporting Time Period: After the Protocol Specified Follow-up Period	Timeframe to Report Event and Follow-up Information to MSD:
Non-Serious Adverse Event (NSAE)	Report if: - due to protocol-specified intervention - causes exclusion - participant is receiving placebo run-in or other run-in treatment	Report all	Not required	Per data entry guidelines
Serious Adverse Event (SAE) including Cancer and Overdose	Report if: - due to protocol-specified intervention - causes exclusion - participant is receiving placebo run-in or other run-in treatment	Report all	Report if: - drug/vaccine related. (Follow ongoing to outcome)	Within 24 hours of learning of event
Pregnancy/Lactation Exposure	Report if: - due to intervention - causes exclusion	Report all	Previously reported – Follow to completion/termination; report outcome	Within 24 hours of learning of event
Event of Clinical Interest (require regulatory reporting)	Report if: - due to intervention - causes exclusion	Report - Potential DILI - Require regulatory reporting	Not required	Within 24 hours of learning of event
Event of Clinical Interest (Do not require regulatory reporting)	Report if: - due to intervention - causes exclusion	Report - non-DILI ECIs and those not requiring regulatory reporting	Not required	Within 5 calendar days of learning of event

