8. A male participant must agree to use a contraception as detailed in Appendix 2 of this protocol during the treatment period and for at least 120 days after the last dose of study treatment and refrain from donating sperm during this period.

Female participants:

- A female participant is eligible to participate if she is not pregnant (see Appendix 2), not breastfeeding, and at least one of the following conditions applies:
 - a.) Not a woman of childbearing potential (WOCBP) as defined in Appendix 2OR
 - b.) A WOCBP who agrees to follow the contraceptive guidance in Appendix 2 during the treatment period and for at least 120 days (corresponding to time needed to eliminate any study treatments (MK-3475 and epacadostat) after the last dose of study treatment.

Informed Consent

9. The participant (or legally acceptable representative if applicable) provides written informed consent for the trial.

Laboratory Values

10. Have adequate organ function as defined in the following table (Table 1). Specimens must be collected within 14 days prior to randomization.

Table 1 Adequate Organ Function Laboratory Values

System	Laboratory Value
Hematological	
Absolute neutrophil count (ANC)	$\geq 1500/\mu\text{L}$
Platelets	$\geq 100\,000/\mu\text{L}$
Hemoglobin	$\geq 9.0\text{ g/dL}$ or $\geq 5.6\text{ mmol/L}^{\text{a}}$
Renal	
Creatinine OR Measured or calculated ^b creatinine clearance (GFR can also be used in place of creatinine or CrCl)	$\leq 1.5 \times \text{ULN}$ OR $\geq 30\text{ mL/min}$ for participant with creatinine levels $> 1.5 \times$ institutional ULN
Hepatic	
Total bilirubin	$\leq 1.5 \times \text{ULN}$ OR direct bilirubin $\leq \text{ULN}$ for participants with total bilirubin levels $> 1.5 \times \text{ULN}$. If there is no institutional ULN, then direct bilirubin should be $< 40\%$ of the total bilirubin. In no case can total bilirubin exceed $3.0 \times \text{ULN}$.
AST (SGOT) and ALT (SGPT)	$\leq 2.5 \times \text{ULN}$
Coagulation	
International normalized ratio (INR) OR prothrombin time (PT) Activated partial thromboplastin time (aPTT) or partial thromboplastin time (PTT) ^c	$\leq 1.5 \times \text{ULN}$ unless participant is receiving anticoagulant therapy as long as PT or aPTT is within therapeutic range of intended use of anticoagulants

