24. Is pregnant or breastfeeding or expecting to conceive or father children within the projected duration of the study, starting with the screening visit through 120 days after the last dose of study treatment.

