6.3.2 Contraception

Pembrolizumab may have adverse effects on a fetus in utero. Furthermore, it is not known if pembrolizumab has transient adverse effects on the composition of sperm.

Developmental and reproductive toxicity studies have not been performed with epacadostat. Epacadostat should not be used by pregnant women.

Participants should be informed that taking the study medication may involve unknown risks to the fetus (unborn baby) if pregnancy were to occur during the study. In order to participate in the study, participants of childbearing potential must adhere to the contraception requirements from the day of study medication initiation (or 14 days prior to the initiation of study treatment for oral contraception) throughout the study period up to 120 days after the last dose of study medication. If there is any question that a participant of childbearing potential will not reliably comply with the requirements for contraception, that participant should not be entered into the study.

Definitions of WOCBP and standards for adequate contraception are outlined in Appendix 2.

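### The pregnancy reporting window in Section 9.3.1 falls from 120 to 30 days once new anticancer therapy starts, although the protocol's own drug-elimination and contraception period stays at 120 days

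*Combined protocol and SAP*

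**What the plan says.** The rule is in Section 9.3.1. For pregnancies and breastfeeding exposures, counted from randomization, the window is worded as follows: "through 120 days following cessation of study treatment, or 30 days following cessation of study treatment if the participant initiates new anticancer therapy must be". The duty falls on the investigator. The AE bullet in the same list uses the same trigger with a 90-day default, but adds a tie-break: "or 30 days following cessation of study treatment if the participant initiates new anticancer therapy, whichever is earlier, must be reported by the investigator". The pregnancy bullet has no tie-break.

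Elsewhere the protocol uses 120 days after the last dose, with no exception for new therapy:

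- Section 6.1, women of childbearing potential: contraception on treatment and "for at least 120 days (corresponding to time needed to eliminate any study treatments (MK-3475 and epacadostat) after the last dose of study treatment".
- Section 6.1, men: also 120 days, without the elimination reason.
- Section 6.2, criterion 24: excludes anyone expecting to conceive or father a child in a period "starting with the screening visit through 120 days after the last dose of study treatment".
- Section 6.3.2: contraception is required "throughout the study period up to 120 days after the last dose of study medication".

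Once the reporting window has closed, three statements in Section 9.3.1 and Table 8 apply. An SAE that comes to the investigator's attention "must be reported immediately to MSD if the event is considered to be drug-related". There is no duty to search: "Investigators are not obligated to actively seek AE or SAE or other reportable safety events in former study participants". For pregnancy and lactation exposure after the follow-up period, Table 8 has one entry: "Previously reported – Follow to completion/termination; report outcome".

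**The concern.** The reporting window and the exposure window should match, and for some participants they do not. Starting another anticancer drug does not speed the elimination of pembrolizumab or epacadostat. A conception on day 60 after the last dose falls within the period that Section 6.1 ties to elimination, whatever the participant has since started.

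For AEs and SAEs, an early cut at new therapy has a rationale: the new drug confounds attribution. Pregnancy reporting serves a different purpose. It records exposure, and Section 9.3.6 says that pregnancy is not itself an adverse event but is reportable all the same. The report also starts the follow-up, because Section 9.3.6 requires every reported pregnancy to be followed to its end. If there is no report, nothing in the protocol starts that follow-up.

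The information is scarce. Section 6.3.2 says that pembrolizumab may harm a fetus and that reproductive toxicity studies of epacadostat have not been done.

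**Working it through.** This is a comparison of time windows. The plan states no figure to reproduce, and the only arithmetic is a subtraction.

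**Inputs**

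| Item | Days after last dose | Source |
|---|---|---|
| Pregnancy reporting, no new therapy | 120 | 9.3.1 |
| Pregnancy reporting, new therapy started | 30 | 9.3.1 |
| Time needed to eliminate both drugs | 120 | 6.1, female criterion |
| Contraception, and conception period in criterion 24 | 120 | 6.1, 6.2, 6.3.2 |
| Safety Follow-up Visit (last visit) | 30 (+7), or before new therapy if sooner | 9.9.5.1 |

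**Length of the gap.** 120 − 30 = 90 days, that is, days 31 to 120. As a share of the window this is 90/120 = 75%. That is a ratio of two windows. It is not a share of pregnancies missed.

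**Which pregnancies fall in it.** I read the bullet as dating a pregnancy by when it begins. A pregnancy that began on treatment or by day 30 is then inside the window even if the site hears of it later. What remains is a participant's conception on days 31 to 120 when she has started new therapy.

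**Could another provision catch it?**

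1. *Table 8.* After the follow-up period it lists only pregnancies already reported. A new one has no entry.
2. *Section 6.3.3, participants.* It applies to a pregnancy that arises on treatment, so not here.
3. *Section 6.3.3, partners.* A male participant's partner pregnancy must be reported, and no time limit is stated there. Partner pregnancies are therefore not part of the gap.
4. *Drug-related SAEs.* These are reportable at any time, and Appendix 3 counts a congenital anomaly as an SAE whenever it is diagnosed. An uneventful pregnancy, or an outcome judged unrelated, does not qualify.
5. *Section 9.3.6.* It makes spontaneously reported pregnancies in the course of the trial reportable, with no cut at new therapy. Under Section 5.3 the overall study ends with the last participant, which would cover most of days 31 to 120. Under Section 9.9.5.1 a participant has completed the study at the Safety Follow-up Visit, by about day 37 (30 + 7), which would cover almost none. The synopsis entry on duration of participation only points back to Section 9.3. The text does not settle which reading applies.

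**Breastfeeding.** Participants are neither pregnant nor breastfeeding at entry (Sections 6.1 and 6.3.4). For a birth by day 120 to follow a conception after the last dose, gestation would have to be under 120 days, which is not viable. A first breastfeeding exposure on days 31 to 120 therefore normally implies conception on treatment. At term (assumed to be about nine months, with 120 days taken as about four), conception would be about 9 − 4 = 5 months or more before the last dose. That pregnancy is already reportable under 9.3.1, and under 9.3.6 it is followed to its end with the infant's health reported.

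**Missing tie-break.** Suppose new therapy starts on day 60. A conception on day 50 was inside a 120-day window when it occurred and lies outside a 30-day one. The bullet does not say which governs. Thirty days is still its natural reading, so this is a secondary drafting point.

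**After the fix.** With one 120-day window, the gap is 120 − 120 = 0 days.

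**The case against.** The strongest reply is that the gap is narrow and may already be closed. Section 9.3.6 has no new-therapy cut, and Section 5.3 supports reading it to the end of the overall study. Treatment can run to 35 cycles plus 17 on retreatment, so the study may stay open well past day 120 for most participants. This reading is fair, and it is why the point can claim only that there is no *clear* duty. It does not remove the problem: on that reading the 30-day limit in 9.3.1 contradicts 9.3.6 while the study is open, and a site still cannot tell which rule to follow.

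The 30-day cut is also a consistent convention: AEs, SAEs and, in Section 9.3.7, ECIs all use it. That is true, but the attribution argument behind it does not extend to recording an exposure.

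The amendment would also gain little, because the last visit is at about day 30 and investigators need not search for events. This stands. The change captures only what a site happens to learn.

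A reader might infer more than the documents support:

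- *That serious fetal harm goes unreported.* Drug-related SAEs remain reportable at any time, and Section 9.3.6 classes outcomes such as fetal death and stillbirth as serious.
- *That three quarters of exposed pregnancies are lost.* The 75% compares windows. The documents give no count of women of childbearing potential and no pregnancy rate.
- *That breastfeeding exposure is a comparable loss.* It is in the bullet's wording, but a first exposure in that period is remote.

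**Conclusion.** The inconsistency is real and stands in the current text. For a participant who starts new anticancer therapy, a pregnancy conceived on days 31 to 120 after the last dose has no clear reporting duty, unless it leads to a drug-related SAE or Section 9.3.6 is read to run to the end of the overall study. The interval is up to 90 days.

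The practical size is small. About 85 participants are randomized, contraception is still required throughout the 120 days, and few cases are expected, although the documents give no figure. The effect is on individual safety reports. No rate, comparison or ORR estimate changes.

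The conclusion rests on two assumptions: that the 120 days in Section 6.1 are, as it says, the time needed for elimination, and that a pregnancy is dated by when it begins. It is a low-cost improvement worth making, and not a defect in the trial's analysis.

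**What to change.** In the pregnancy and breastfeeding bullet of Section 9.3.1, delete the clause that substitutes 30 days when new anticancer therapy is started. The window then ends at 120 days for every participant, in line with Sections 6.1, 6.2 and 6.3.2, and the missing tie-break no longer matters. Leave the AE, SAE and ECI windows unchanged.

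The cost is one deleted clause. It adds no visit, test, contact or active search. The downside is an occasional pregnancy report confounded by the later therapy, which can be noted on the report.
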